1 SYNOPSIS

CLINICAL INVESTIGATION TITLE: A Prospective, Randomized, Controlled Study Assessing Vagus Nerve Stimulation in CoViD-19 Respiratory Symptoms (SAVIOR II)

CLINICAL INVESTIGATION CODE:

2020-132-AGH

CLINICAL INVESTIGATIONAL MEDICAL DEVICE(S):

gammaCore Sapphire® (non-invasive vagus nerve stimulator)

OBJECTIVES:

The aims of this study are to summarize and compare the incidence of clinical events and pro-inflammatory cytokine levels in patients randomized to use of gammaCore Sapphire plus standard of care vs standard of care alone in patients hospitalized for CoViD-19. In addition, this study is intended to demonstrate the safety of gammaCore Sapphire use in patients hospitalized for CoViD-19.

Specific clinical events to be summarized include, but are not limited to:

- Changes in oxygen support requirements (no oxygen support, low-flow oxygen support, nasal high-flow oxygen support, noninvasive mechanical ventilation, and invasive mechanical ventilation)
- Changes in O₂ saturation
- PaO₂/FiO₂ ratio
- Proportion of subjects requiring mechanical ventilation
- Days to onset of mechanical ventilation
- Live discharge from the hospital
- Patient length of stay
- Mortality
- Shortness of Breath
- Clinical improvement Scale

Specific laboratory measurements to be summarized include, but are not limited to:

- TNF- α
- IL-1 β
- IL-6
- CRP
- Ferritin
- D Dimer

- Pro-Calcitonin

OVERALL CLINICAL INVESTIGATION DESIGN:

The study is a prospective, randomized, controlled investigation designed for comparison of two groups for the reduction of respiratory distress in a CoViD-19 population, using gammaCore Sapphire® (nVNS) plus standard of care (active) vs. standard of care alone (SoC), the control group. The gammaCore® (nVNS) treatments will be used acutely and prophylactically.

Prophylactic

Administer one treatment of gammaCore®, scheduled three times a day (morning, mid-day and 1 hour before bed at night)

One treatment is defined as 2 consecutive doses (stimulations). Each dose delivers a 2-minute stimulation. One dose is applied to the left side of the neck, then one is applied to the right side

SoC: No Administration of gammaCore®

AND

Acute respiratory failure (w/hypoxia) or Shortness of breath

Administer one treatment of gammaCore® for acute treatment of shortness of breath (as needed, up to nine times a day)

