7 DESIGN OF THE CLINICAL INVESTIGATION

7.1 Overall Clinical Investigation Design

The study is a prospective, randomized, control investigation designed for comparison of two groups for the reduction of respiratory distress in a CoViD-19 population, using gammaCore® Sapphire plus standard of care (active) vs. standard of care alone (SoC), the control group. The gammaCore® treatments will be used acutely and prophylactically.

Figure 1 Overall Design

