7.2 Clinical Investigation Procedures and Definitions

Once the patient is admitted to the hospital, the institution shall follow their standard protocol for their CoVid-19 patients. The investigator shall administer the consent form, conduct the intake and randomize the patient 1:1 into each of the two study arms prior to baseline measurements. Once qualified, the patient shall be trained on the use of gammaCore® and provided an initial treatment. For every day the patient is in the hospital but not on mechanical ventilation, the administration of gammaCore®, prophylactically and acutely, will be recorded on the daily study log as per protocol treatment.

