7.2.2 Clinical Investigation Flow Chart

Procedures and outcome measures will be collected as described in the clinical investigation flow chart shown in Table 1.

Table 1 Clinical Investigation Flow Chart

Protocol requirements	Study Visit (D=Day)								
	Admission/ D0	D1	D2	D3	D4	D5	D6	D7	Study Termination ^e
Informed Consent	X								
Inclusion/ Exclusion criteria	X								
Randomization	X								
Complete physical exam	X								
Enter Device #	X								
Intake ^a	X								
Study Measurements ^b	X	X	X	X	X	X	X	X	X
Pro-Calcitonin, C-reactive protein, ferritin, D-dimer, CBC w/dif	X (+ serum/urine hCG for women who may be pregnant)	X		X		X		X	X
Comprehensive metabolic panel	X			X		X		X	X
Study labs drawn before 10am (Frozen blood sample, Immunokine panel (Luminex) including (TNF- α , IL-1 β , IL-6), Leukocyte flow cytometry		X	X	X		X		X	

Clinical Investigation Plan

	Study Visit (D=Day)									
Protocol requirements	Admission/ D0	D1	D2	D3	D4	D5	D6	D7	Study Termination ^e	
Device training ^c	X									
nVNS Stimulation Supervised ^c	X	X								
VNS Stimulation ^c		3X +prn	X							
Clinical Improvement Scale	X	X	X	X	X	X	X	X	X	
Daily Tx Log completed ^d	X	X	X	X	X	X	X	X	X	
Concomitant medications	X	X	X	X	X	X	X	X	X	
Adverse Event	X	X	X	X	X	X	X	X	X	

- ^a Includes collection of basic demographics (DOB, Race, Sex, Smoking Status, County/Region), medications, comorbidities CoViD-19 test results)
- ^b Includes height/weight (BMI), temperature, blood pressure, O₂ saturation, PaO₂/FiO₂ ratio, shortness of breath assessment, cough assessment
- ^c For the active study arm. Includes record of treatment (time and number of doses administered)
- ^d The following parameters will be recorded daily: Oxygen dependence & data, ventilator dependence & data, discharge data, survival, device treatment record (active study arm only)
- ^e Study completion will be determined by discharge, transition to mechanical ventilation and/or if the patient is unable to continue

7.3 Discussion and Justification of Clinical Investigation Design, Including the Choice of Control Groups

The study design (randomized, including a control group) was chosen to evaluate the usefulness of the gammaCore® Sapphire device for symptom improvement in patients suffering CoViD-19 related respiratory distress compared to standardized institution treatment only.

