7.10.1.1 Data Sets to be Analysed

The intention to treat (ITT) population includes all randomized subjects with at least 1 verified treatment post-training during study period. The ITT population will be analyzed using the subject's randomized treatment regardless of which treatment the subject actually received.

Subjects with major protocol deviations will be excluded from the per-protocol (PP) analysis set. Subjects not taking the study treatment in the prescribed manner more than 33% of the time will be excluded from the PP analysis set. Additional subjects with exclusionary protocol deviations will be identified prior to database finalization and unblinding. Analyses for the PP will be conducted according to the randomized treatment.

All subjects entering the study will be included in the safety population. Analyses for safety population will be conducted according to the treatment actually received.

Definitions

Generally, a baseline measurement refers to the last non-missing assessment made before the first administration of study treatment (at e.g. screening and baseline).

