7.10.1.6 Adverse Events/Adverse Device Effects

Device-related serious adverse events will be tabulated. The overall incidence of device-related serious adverse events will be summarized and presented as a proportion and respective 95% exact binomial confidence interval. Additionally, an overview of events, to include total numbers of events, and total number of subjects with events will be tabulated and presented for all AEs, serious AEs, and device-related AEs and device-related serious AEs, as well as deaths. Events will be presented overall and by study arm.

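### Grouping the safety population by treatment received puts a device-arm patient who never uses the device, with any SAE or death, in the control column, and conflicts with tabulating events by study arm

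*Combined protocol and SAP*

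**What the plan says.** Section 7.10.1.1 sets no exposure requirement for safety: "All subjects entering the study will be included in the safety population". It then fixes the grouping: "Analyses for safety population will be conducted according to the treatment actually received".

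The trial has only two treatments. Section 7.1 describes the device "plus standard of care (active) vs. standard of care alone (SoC), the control group". The Synopsis defines the control regimen by absence: "SoC: No Administration of gammaCore". There is no sham and no separate category for patients who were assigned the device but did not use it.

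The ITT set in the same section is "all randomized subjects with at least 1 verified treatment post-training during study period", analysed as randomised.

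Section 7.10.1.6 covers the tables of AEs, SAEs, device-related events and deaths, and says "Events will be presented overall and by study arm". It does not say whether the arm is the one assigned or the one received. Elsewhere the term refers to assignment. Section 7.2 has the investigator "randomize the patient 1:1 into each of the two study arms prior to baseline measurements", and footnote d of Table 1 in 7.2.2 speaks of the "device treatment record (active study arm only").

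**The concern.** Grouping safety data by treatment received is conventional. It usually does little harm when the control is itself something administered, because a patient who takes nothing is plainly not a control. Here the control treatment is the absence of the device, so non-use alone makes a patient a control, and early deterioration can cause non-use. A reclassification that depends on prognosis moves bad outcomes out of the device column and into the control column.

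What is at stake is the all-cause SAE and death table by arm. The study is intended to demonstrate safety (section 6), and at 30 patients per arm one misplaced patient is visible in that table.

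**Working it through.** The plan gives no event rate, alpha or power (7.10.3), so there is no stated figure to reproduce. The check traces one patient through the rules and then sizes the effect under stated assumptions.

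**1. Can the case arise?** Randomisation comes before baseline measurements (7.2). Section 7.2.1.1 then lists examination, intake, labs, and device training with the first treatment, all on Day 0. Participation ends at mechanical ventilation (7.2.1.5), so a patient ventilated before first use never uses the device on study. Adverse events are assessed on Day 0 (Table 1), so the event would be recorded. The interval is short but it exists.

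**2. Where does the patient go?** Take a patient randomised to the device who has an SAE or dies before any stimulation.

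| Rule | Result for this patient |
|---|---|
| Safety set, membership (7.10.1.1) | Included |
| Safety set, grouping by treatment received (7.10.1.1) | Standard of care alone, so control |
| ITT set (7.10.1.1) | Excluded: no verified post-training treatment |
| Event tables by study arm (7.10.1.6) | Device, if the arm is the assigned one; control, if 7.10.1.1 governs |

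Under 7.10.1.1 the event is in the device column of neither analysis set. Under the ordinary meaning of study arm in 7.10.1.6 it is in the device column. The two sections give different answers. The plan also does not say whether the training stimulation counts as having received the device.

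**3. Size.** Inputs: 30 per arm (7.4.1); *e* events in each arm as randomised (assumed, equal in both arms); one device-arm patient with an event moved to control.

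Shift = (*e* − 1)/29 − (*e* + 1)/31 = (2*e* − 60)/899.

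| *e* per arm | As randomised | As received: device v control | Shift (points) |
|---|---|---|---|
| 3 (assumed) | 10.0% v 10.0% | 2/29 = 6.9% v 4/31 = 12.9% | −6.0 |
| 6 (assumed) | 20.0% v 20.0% | 5/29 = 17.2% v 7/31 = 22.6% | −5.3 |

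The only in-trial figure is one SAE in the first 20 patients (7.10.4): 1/20 = 5%, or 0.05 × 30 = 1.5 expected per arm. Putting *e* = 1 and *e* = 2 into the formula gives −58/899 = −6.5 and −56/899 = −6.2 points, so the shift per moved patient hardly depends on the event rate. The event rate does limit how many patients could be moved.

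The direction depends on the moved patient having an event. A refuser without an event changes only denominators: at *e* = 3, 3/29 − 3/31 = 10.3% − 9.7% = +0.7 points, slightly against the device.

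**4. Primary safety measure.** Section 7.7.3 names related SAEs, and 7.10.1.6 reports device-related SAEs as a proportion with an exact 95% interval. An event before first use cannot be device-related, so the numerator is unchanged. With zero events in the device arm the upper limit is 1 − 0.025^(1/n): 11.6% for n = 30 and 11.9% for n = 29. The difference is negligible.

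**The case against.** The strongest reply is that no sentence in the plan says never-users are counted as controls. This is an inference from definitions, and 7.10.1.6 can be read as already tabulating by assigned arm. That is fair. But it leaves two sections giving different answers, and 7.10.1.1 is the one that names the safety population. Section 7.10.1 defers detail to a separate SAP that is not among the documents; never-users could be dealt with there, but nothing available does so.

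The second reply is that it will rarely happen. First use is supervised on Day 0, staff may assist or administer (7.3, 7.6), and eligible patients have already agreed to use the device (7.4.2). This stands: no affected patient at all is a likely outcome, and one is the reasonable illustration.

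The third is that little depends on it, since the primary measure is almost untouched and 7.10.1.2 calls all comparisons nominal. This also stands and limits the weight of the point. A descriptive table with a patient in the wrong column still misleads its reader.

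Three stronger readings are tempting and are not supported:

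- A reader might infer that the safety tables are the only randomised evidence on harm. Mortality and mechanical ventilation are also listed outcomes (section 6, 7.7.2), and the ITT set is grouped as randomised. Its entry rule is defective, but it drops never-users rather than moving them to control.
- A reader might infer from footnotes c and d of Table 1 that a control who used the device could not be detected. Medical records must hold treatments and the device serial number (7.9.2), and deviations are recorded with an explanation (7.12), so a crossover could surface.
- A reader might extend the arithmetic to two or three moved patients and quote a much larger bias. With about 1.5 SAEs expected per arm at the observed 5%, and only the interval before first use on Day 0 in which to have them, that is not a realistic case. One in 20 is an imprecise estimate, but nothing in the documents supports the larger figures.

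**Conclusion.** The point holds as a gap and a conflict between 7.10.1.1 and 7.10.1.6, not as a demonstrated bias. Read literally, a patient assigned to the device who never uses it is analysed for safety as a control and is absent from ITT. If one such patient has an SAE or dies, the all-cause difference moves by about 5 to 6 percentage points in the device's favour. That size assumes 30 per arm and 3 to 6 events in each arm, equal before the move; the documents supply neither event rates nor the number of never-users. The effect on device-related SAEs is negligible. The change is worth making because the misplacement depends on prognosis and is easily removed.

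**What to change.** In 7.10.1.1 and 7.10.1.6:

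- State that all-cause AEs, SAEs and deaths are tabulated by randomised arm, for all randomised patients, from randomisation onwards.
- Restrict grouping by received treatment to device-related events, with patients who had at least one stimulation as the denominator, and say whether the training stimulation counts.
- List patients whose received treatment differs from the assigned one, including never-users.

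The cost is a few sentences, one short listing and a second denominator to label clearly. No extra patients, procedures or data fields are needed.

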7.10.1.2 Summary Statistics

Data will be presented using summary statistics. For example, categorical data may be presented as proportions and counts; continuous data may be presented with the mean, median, minimum, maximum, and/or standard deviations. Kaplan-Meier methodology may be used to present time to event data. All comparisons between active and control groups are nominal in nature; confidence intervals and p-values may be presented, but are not intended for inferential purposes.

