 - Total number of gammaCore® treatments administered with Date/time
- Daily Tx Log
 - Oxygen Requirements, Oxygen level (%), Ventilator Dependence, Date and time of Ventilation, Patient discharge home, (if applicable) Date and time of Discharge, Survival
- Clinical Improvement Ordinal Scale
- Concomitant medication and adverse event assessments

All Odd Days Starting Day 5

Same as Days 1 and 3

Study Completion

The last day of the study will be determined by discharge, transition to mechanical ventilation and/or if the patient is unable to continue i.e. death or feasibility impossible. The following will be recorded:

- Study Measurements:
 - Height/Wt, BMI, Temperature, Blood Pressure, O₂ Saturation, PaO₂/FiO₂ ratio, Shortness of Breath, Cough
- Labs (Standard of care)
 - Pro-Calcitonin, C-reactive protein, Ferritin, D-Dimer, CBC with differential,

Comprehensive metabolic panel

- Labs (Research) Early am blood draw (before 10 am)
 - TNF- α , IL-1 β , IL-6
- VNS stimulations
 - Total number of gammaCore® treatments administered, dates/times
- Daily Tx Log
 - Oxygen Required, Oxygen level (%) based on device type (HFNC / NC / Bipap / Optiflow), Ventilator Dependence (Yes / No), Date and time of Ventilation, Patient discharge home (Yes / No), Date and time (in 24 hour format) of Discharge, Survival (Yes / No) with Date and Time of Death
- Clinical Improvement Ordinal Scale
 - Concomitant medication and adverse events assessment

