6 CLINICAL INVESTIGATION OBJECTIVES

The aims of this study are to summarize and compare the incidence of clinical events and pro-inflammatory cytokine levels in patients randomized to use of gammaCore Sapphire plus standard of care vs standard of care alone in patients hospitalized for CoViD-19. In addition, this study is intended to demonstrate the safety of gammaCore Sapphire use in patients hospitalized for CoViD-19.

Specific clinical events to be summarized include, but are not limited to:

- Changes in oxygen support requirements (no oxygen support, low-flow oxygen support, nasal high-flow oxygen support, noninvasive mechanical ventilation, and invasive mechanical ventilation)
- Changes in O₂ saturation
- PaO₂/FiO₂ ratio
- Proportion of subjects requiring mechanical ventilation
- Days to onset of mechanical ventilation
- Live discharge from the hospital
- Patient length of stay
- Mortality
- Shortness of Breath
- Clinical improvement Scale

Specific laboratory measurements to be summarized include, but are not limited to:

[figure not shown]
- TNF- α
- IL-1 β
- IL-6
- CRP
- Ferritin
- D Dimer
- Pro-Calcitonin

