7.2.1.5 Day of Study Completion

The last day of the study will be determined by discharge, transition to mechanical ventilation and/or if the patient is unable to continue. The following will be recorded:

- Study Measurements
 - Height/Wt, BMI
 - Temperature
 - Blood Pressure
 - O₂ Saturation
 - PaO₂/FiO₂ ratio
 - Shortness of Breath (Yes / No)
 - Cough (Yes / No)
- Labs
 - Pro-Calcitonin
 - C-reactive protein

Clinical Investigation Plan

- Ferritin
- D Dimer
- CBC with differential
- Comprehensive metabolic panel
- nVNS stimulations
 - Total number of gammaCore® treatments administered
 - Date and time of stimulations
- Daily Tx Log
 - Oxygen Required (Yes / No)
 - Oxygen level (%) based on device type (HFNC / NC / Bipap / Optiflow)
 - Ventilator Dependence (Yes / No)
 - Date and time of Ventilation
 - Patient discharge home (Yes / No)
 - Date and time (in 24 hour format) of Discharge
 - Survival (Yes / No) with Date and Time of Death
- Clinical Improvement Scale
 - Concomitant medication assessment
 - Adverse event assessment

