7.7.2 Objectives

The aims of this study are to summarize and compare the incidence of clinical events and pro-inflammatory cytokine levels in patients randomized to use of gammaCore Sapphire plus standard of care vs standard of care alone in patients hospitalized for CoViD-19. In addition, this study is intended to demonstrate the safety of gammaCore Sapphire use in patients hospitalized for CoViD-19.

Specific clinical events to be summarized include, but are not limited to:

- Changes in oxygen support requirements (no oxygen support, low-flow oxygen support, nasal high-flow oxygen support, noninvasive mechanical ventilation, and invasive mechanical ventilation)
- Changes in O₂ saturation
- PaO₂/FiO₂ ratio
- Proportion of subjects requiring mechanical ventilation
- Days to onset of mechanical ventilation
- Live discharge from the hospital
- Patient length of stay
- Mortality
- Shortness of Breath
- Clinical improvement Scale

Specific laboratory measurements to be summarized include, but are not limited to:

- TNF- α
- IL-1 β
- IL-6
- CRP
- Ferritin
- D Dimer
- Pro-Calcitonin
-

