7.10 Statistical Methods and Determination of Sample Size

7.10.1 Statistical Evaluation of Performance and Safety Variables

This section provides a summary of the statistical methodology that will be used by the Institution. A more detailed description of analysis methods will be provided in a separate statistical analysis plan (SAP).

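### Kaplan-Meier is the only time-to-event method named, but discharge ends observation: a standard curve for days to ventilation would overstate absolute ventilation risk

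*Combined protocol and SAP*

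**What the plan says.** Section 7.10.1.2 (Summary Statistics) states that "Kaplan-Meier methodology may be used to present time to event data". Section 7.10.3 repeats the sentence. No other time-to-event method appears, and no endpoint is attached to this one. Section 7.10.1 describes itself as a summary, and 7.10.1.3 leaves the analysis of the objectives to a separate SAP.

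The outcomes in Sections 6 and 7.7.2 include "Days to onset of mechanical ventilation", "Proportion of subjects requiring mechanical ventilation" and "Live discharge from the hospital", together with length of stay and mortality.

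On the end of observation, Section 7.2.1.5 says: "The last day of the study will be determined by discharge, transition to mechanical ventilation and/or if the patient is unable to continue". Footnote e of the flow chart in 7.2.2 gives the same rule. The Synopsis, under Study Completion, adds death: "transition to mechanical ventilation and/or if the patient is unable to continue i.e. death or feasibility impossible". No visit after discharge is scheduled. Section 7.10.2 (drop-outs and missing data) gives no censoring rule, and no section names a competing event or a time horizon.

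**The concern.** The Kaplan-Meier complement (1 − KM) can be read as absolute risk only if censored patients have the same later risk as those still under observation. Under this stopping rule almost every patient who leaves without ventilation leaves because of live discharge, that is, because of recovery. Discharge is therefore a competing event. Censoring it asks what would happen if nobody could go home. Death before ventilation is a second competing event.

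Two things are at stake.

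- **Absolute risk.** One report could show a ventilation curve well above its own crude proportion ventilated, with no stated reason.
- **Comparison of arms.** Section 7.6 anticipates fewer hospital days with the device. If the device only speeds discharge and leaves the daily ventilation risk unchanged, the two Kaplan-Meier curves coincide although fewer device patients are ventilated.

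The mirror problem affects time to live discharge, where deaths would be censored, and so would ventilated patients if ventilation ends observation. Whether discharge after ventilation is recorded is unclear: 7.2.1.5 and 7.2.2 end the study at ventilation, while 7.10.4 describes the first 20 patients as having completed their hospital stay.

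**Working it through.** The plan contains no event rate, hazard or curve to reproduce, so every rate below is an assumption. The one input from the documents is 30 patients per arm (Section 7.4.1). Deaths and withdrawals are set to zero.

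**A small worked arm.** Take 30 patients: 6 ventilated, on days 2, 3, 4, 5, 7 and 10, and 24 discharged between days 3 and 16. With illustrative discharge dates that leave 30, 29, 27, 24, 17 and 8 patients at risk at the six ventilations:

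1 − KM = 1 − (29/30)(28/29)(26/27)(23/24)(16/17)(7/8) = 29.1%

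The proportion actually ventilated is 6/30 = 20.0%.

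**Constant daily risks.** Let v be the daily risk of ventilation and d the daily risk of discharge.

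- True proportion ventilated by day t: [v/(v+d)] × [1 − (1−v−d)^t]
- Kaplan-Meier with discharge censored: 1 − (1−v)^t
- Expected number still at risk: 30 × (1−v−d)^t

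With v = 0.03 and d = 0.12:

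| Day | True | Kaplan-Meier | At risk, of 30 |
|---|---|---|---|
| 7 | 0.2 × (1 − 0.85^7) = 13.6% | 1 − 0.97^7 = 19.2% | 9.6 |
| 14 | 0.2 × (1 − 0.85^14) = 17.9% | 1 − 0.97^14 = 34.7% | 3.1 |

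**Range.** With v of 1, 2, 3 or 5% and d of 8, 10, 12, 15 or 20% (20 combinations), the day-7 overstatement is 1.26- to 1.77-fold, with at least 4.0 of 30 at risk throughout. In absolute terms the gap is 1.4 to 12.8 points. At day 14 it is 1.55- to 2.30-fold in the 14 combinations with more than 2 of 30 at risk; the other 6 are set aside.

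A separate continuous-time calculation, assuming 10–30% eventually ventilated and a median of 5–10 days to the end of observation, gives 1.36- to 2.06-fold at day 14.

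**Risk that is not constant.** Here the true figure is the sum over days of (proportion still at risk) × v, and Kaplan-Meier is 1 minus the product of the daily (1 − v).

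| Assumed pattern | True, day 14 | Kaplan-Meier, day 14 | Ratio |
|---|---|---|---|
| v = 6% on day 1, falling 20% a day; d = 12% | 18.1% | 25.3% | 1.40 |
| v = 5% on days 1–5 only; d = 12% | 17.8% | 22.6% | 1.27 |
| v = 6% on days 1–3 only; d = 5% | 16.1% | 16.9% | 1.05 |
| v = 5% on days 1–5; no discharge before day 6 | 22.6% | 22.6% | 1.00 |

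**At this sample size.** In 20,000 simulated arms of 30 per pattern, the day-14 Kaplan-Meier estimate was at least 10 points above the crude proportion in 67% of arms (constant 3%/12%), 23% (declining), 6% (days 1–5 only) and 0% (days 1–3 only). At day 7 the first three were 13%, 7% and 6%.

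**Two arms.** Ventilation 3% a day in both, discharge 8% against 12% a day:

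- True by day 14: (0.03/0.11)(1 − 0.89^14) = 21.9% against 17.9%.
- Kaplan-Meier: 34.7% in both, because d does not enter its formula.
- At risk at day 14: 5.9 and 3.1 of 30.

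**Mirror, if ventilation ends observation.** At 3%/12%, the proportion discharged without prior ventilation by day 14 is 0.8 × (1 − 0.85^14) = 71.8%. Kaplan-Meier with ventilation censored gives 1 − 0.88^14 = 83.3%.

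**The case against.** The strongest reply is that no error is in the text. The sentence is permissive, stands among examples, attaches no endpoint, and leaves detail to an SAP not available here. Days to ventilation could be summarised as a mean or median with no curve. Kaplan-Meier itself would return the crude proportion if discharged patients were kept event-free in the risk set to a fixed horizon. The undistorted proportion is already listed, comparisons are declared nominal in 7.10.1.2, and no test, error rate or sample size depends on the curve. The two-arm example is partly a choice of estimand, since coinciding curves correctly report equal daily risks. The magnitudes come from assumed rates, and in the day-7 grid 18 of 20 gaps are under 10 points.

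Most of this stands, and it limits the weight of the point. It does not remove it. The protocol steers the SAP to one method, and the usual application of that method is wrong under the protocol's own stopping rule. Descriptive displays are what this trial will produce, so a curve readily read as absolute risk matters even without a test. Listing the crude proportion as well means the conflict could appear within one report.

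**Conclusion.** The concern holds as a conditional one: if Kaplan-Meier is used in the standard way for days to ventilation, it overstates absolute risk whenever some discharges precede later ventilations. The direction is secure. The size is not, because the documents give no rates. Under the assumptions above it runs from no bias (all ventilation before any discharge) to about twofold at day 14 in the constant 3%/12% case, and up to 2.30-fold in the combinations retained. The larger figures come from steady risk throughout the stay and few patients left at risk; early, short-lived risk gives little bias.

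The consequence is a misleading display and a possibly hidden difference between arms. No hypothesis test is lost. It should be corrected because the correction is cheap and is best made before the SAP is fixed.

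**What to change.** In 7.10.1.2 and 7.10.3, or in the SAP, replace the Kaplan-Meier sentence with:

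> Time to in-hospital mechanical ventilation will be shown by arm as Aalen-Johansen cumulative incidence to a fixed in-hospital horizon set before data review, with live discharge and death before ventilation as competing events; only withdrawals are censored, and numbers at risk are shown. Time to live discharge will be shown the same way, with death as a competing event, and with ventilation as a competing event only if discharge after ventilation is not recorded; in that case it is labelled discharge without prior ventilation.

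State in the same place whether discharge after ventilation is recorded, and that patients unable to continue for reasons other than death count as withdrawals. Without withdrawals, the ventilation curve then ends at the simple proportion ventilated by the horizon. The listed proportion should carry the same horizon if the two displays are to match.

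The cost is wording in two sections or the SAP and slightly more programming. Section 7.2.1.5 already collects dates and times of ventilation, discharge and death, and no follow-up after discharge is needed. Displayed ventilation curves will be lower. If discharge after ventilation is not recorded, the discharge curve describes something narrower than the listed live-discharge outcome, and the report should say so.
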